### 9.2 Adverse events

Adverse events are recorded on the Adverse Event CRF as they occur, from the time informed consent is granted until study completion or study termination (end of the SFU period 30 days after the last IMP intake). Also, adverse events ongoing at the Entry Visit in EP0093 will be recorded in the Adverse Event\_Parent Study CRF.

A treatment-emergent adverse event (TEAE) is defined as any event not present prior to the initiation of the first dose of study treatment in this study or any unresolved event already present

before initiation of the first dose that worsens in intensity following exposure to the treatment. TEAEs are AEs with start dates on or after the date of first dose of PSL in EP0093. The number and percentage of subjects who experience TEAEs at any time during the study will be summarized (using the SS) by SOC and PT.

Unless noted otherwise, TEAEs during the study will be summarized. At the time of a clinical cutoff, TEAEs with onset date prior to or on the clinical cutoff date will be included. TEAEs are assigned into an analysis period or time interval based on the start date. Adverse event summaries will be ordered in terms of decreasing frequency for SOC, and PT within SOC. The following tabular summaries will be presented for the SS:

- Ongoing AEs at EP0093 study entry
- Incidence of TEAEs during the Study – Overview by Region
- Incidence of TEAEs by Region
- Incidence of TEAEs by 3-month time interval during the Exposure Period
- Incidence of Serious TEAEs
- Incidence of TEAEs by Relationship
- Incidence of SAEs by Relationship. Of note, this table is needed for data transparency reporting.
- Incidence of Fatal TEAEs by Relationship. Of note, this table is needed for data transparency reporting.
- Incidence of TEAEs by Maximum Intensity
- Incidence of TEAEs leading to discontinuation (ie, drop out)
- Incidence of TEAEs leading to dose reduction
- Incidence of TEAEs occurring in at least 5% of Subjects
- Incidence of TEAEs by Dose at Onset ( $\leq 200\text{mg/day}$ ,  $>200\text{mg/day}$  to  $\leq 400\text{mg/day}$ ,  $>400\text{mg/day}$  to  $\leq 600\text{mg/day}$ , and  $>600\text{mg/day}$ ) during the Exposure Period.
- Incidence of Non-Serious TEAEs above the Threshold of 5% of Subjects. This table is needed for data transparency reporting.

Summary tables will contain counts of subjects, percentages of subjects in parentheses and the number of events where applicable. A subject who has multiple events in the same SOC and PT will be counted only once in the subject counts, but all events will be included.

In summaries of relationship to study treatment per the investigator, the following relationships will be summarized: 'Not related', 'Related'. Events with missing relationship will be considered as 'Related' for summary purposes but recorded as missing in the listings.

In summaries of maximum intensity, the following intensity categories will be summarized: 'Mild', 'Moderate', 'Severe'. Subjects who experience the same event multiple times will be included in the most severe category. Events with missing intensity will be considered as 'Severe' events for summary purposes but recorded as missing in the listings.

Listings will be provided for AEs, SAEs, AEs leading to discontinuation (ie, drop out), and AEs leading to death by subject for the SS.

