4 STUDY VARIABLES

4.1 Safety variables

4.1.1 Primary safety variables

The primary safety variables are the following:

- Incidence of TEAEs reported by the subject and/or caregiver or observed by the Investigator
- Incidence of TEAEs leading to study withdrawal

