12.3 Planned safety analyses

All safety variables will be analyzed by descriptive methods and listed on the SS.

Treatment-emergent AEs will be summarized by study period (Evaluation, Taper, and SFU) and reported for cumulative 3-month time intervals and categories of total duration of exposure, using the Medical Dictionary for Regulatory Activities (MedDRA[®]) primary System Organ Class (SOC) and Preferred Term in incidence tables. Separate tables will be provided for AEs leading to withdrawal from the study and SAEs overall and by the subcategories listed above.

Laboratory values, ECG data (heart rate, PR interval, QTcB, QTcF, and QRS interval), vital signs, and weight will be summarized by period and visit (actual values and change from Entry Visit). Possible clinically significant treatment-emergent abnormalities for laboratory values,

vital signs, and weight will be listed and summarized by period and visit. Electrocardiogram abnormalities will also be listed by period and visit.

Summary tables (and graphical outputs if needed) will be performed on the Doppler echocardiography data.

Physical and neurological examinations, psychiatric assessments and the withdrawal symptoms using the CIWA-B assessment will be provided as listing by period and visit (actual values and change from Entry Visit). The C-SSRS results will be displayed in a listing.

Any additional listings or tabulations will be described in the SAP.

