**Table 3–3.21: Start and end of EP0093 analysis periods**

Description	Start	End	Details
Evaluation Period	Entry Visit (EV, Visit 1)	EOS or EDV or the last contact date if neither EOS or EDV visit is available.  At the time of a clinical cutoff prior to the study completion, if a subject is ongoing and doesn't have the EDV, the end of the period is set to the clinical cutoff date.	The Entry Visit (EV, Visit 1) will be done on the same day as the last visit of the parent study. Subjects will return to clinic every 2 weeks during Month 1, every month during Month 2-3, every 3 months after Month 3 up to Month 24.
Taper Period/ Safety Follow-Up Period	1 day after end date of evaluation period.	The date of final contact.  At the time of a clinical cutoff prior to the study completion, if a subject is ongoing, the end of the period is set to the clinical cutoff date.	Applies only to patients who discontinue the study or complete it without continuation of PSL treatment.
Exposure Period	Date of first dose of PSL	Date of last dose of PSL	Extends from the date of first dose until the last dose of PSL in EP0093. It may include the Evaluation and Taper Period. (Section 3.2.2.1).

At the time of a clinical cutoff prior to the study completion, subjects without the Study Termination eCRF will be classified as “ongoing.” Only the data on or prior to the clinical cutoff date will be included in the analyses.

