### 3.2.5 Interval duration

A month is defined as 30 days and time intervals based on monthly durations are defined as a multiple of 30 days (eg, 12 months is defined as 360 days).

Interval Duration Definition:

- Months 0-3 Days 1-90
- Months >3-6 Days 91-180
- Months >6-9 Days 181-270
- Months >9-12 Days 271-360

Subsequent intervals are defined in a similar manner. For the analysis of seizure data during the Evaluation Period, 3-month intervals will be derived for the Evaluation Period. For the analysis of AEs and safety variables, 3-month intervals will be derived for the Exposure Period.

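### TEAE withdrawals and serious and fatal TEAEs are planned as Safety Set percentages with no time split or time at risk, and the protocol's time-based AE tables are left out undeclared

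*SAP*

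**What the plan says.** Protocol 4.1.1 names two primary safety variables: the incidence of TEAEs, and "Incidence of TEAEs leading to study withdrawal". Protocol 12.3 then sets the layout: "Treatment-emergent AEs will be summarized by study period (Evaluation, Taper, and SFU"), with further splits by cumulative 3-month interval and by category of total exposure. It asks for AEs leading to withdrawal and SAEs overall and by those same splits. Protocol 12.6 gives the reason: subjects leave at different times.

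SAP 9.2 sets the measure: the "number and percentage of subjects who experience TEAEs at any time during the study will be summarized". It lists 14 tables on the Safety Set, which needs one dose (SAP 3.5.2). One of them is split by time: "Incidence of TEAEs by 3-month time interval during the Exposure Period". The content of the tables is fixed: "Summary tables will contain counts of subjects, percentages of subjects in parentheses and the number of events where applicable". AEs are collected "until study completion or study termination (end of the SFU period 30 days after the last IMP intake"), whereas the Exposure Period in SAP Table 3–3.21 "Extends from the date of first dose until the last dose of PSL in EP0093". SAP 3.2.5 adds: "For the analysis of AEs and safety variables, 3-month intervals will be derived for the Exposure Period", and defines those intervals as separate blocks (days 1-90, 91-180 and so on).

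**The concern.** The primary objective is long-term safety. When follow-up differs between subjects, the percentage with an event mixes how often events occur with how long people were watched. SAP 3.9 records that the study was terminated early, so follow-up well short of 24 months, and uneven, is likely. SAP 9.2 shows the TEAE overview and the TEAE table by region, and the SAP Addendum repeats every table for Japan and non-Japan. If those groups entered at different times, their percentages rest on different follow-up and cannot be compared directly. For withdrawal, serious and fatal events, no planned table would let a reader see or allow for that.

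**Working it through.** **Inputs.** The documents give no event rate, exposure distribution or expected incidence, so there is no plan figure to reproduce. The table comparison below rests on the documents alone. Every hazard, exposure pattern and sample size after it is an assumption.

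**1. Protocol 12.3 against SAP 9.2.**

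| Split in protocol 12.3 | All TEAEs in SAP 9.2 | Withdrawal TEAEs | Serious TEAEs |
|---|---|---|---|
| Study period | not listed | not listed | not listed |
| 3-month interval (protocol: cumulative) | listed, separate intervals | not listed | not listed |
| Total-exposure category | not listed | not listed | not listed |

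Fatal TEAEs appear by relationship only. SAP 5.1 adds a count and percentage of subjects discontinuing for AEs, again without time. SAP 3.9 details the removal of AED drug load but mentions no AE table.

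**2. Effect of follow-up on a percentage, sustained hazard.** With constant rate r per subject-year and follow-up t years, the percentage is 1 − exp(−r·t). At r = 0.20:
- 6 months: 1 − exp(−0.1) = 9.5%
- 18 months: 1 − exp(−0.3) = 25.9%

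Averaged over three exposure patterns:

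| r per subject-year | all 24 months | uniform 3-24 months | uniform 1-12 months | rate per 100 subject-years, all three |
|---|---|---|---|---|
| 0.05 | 9.5% | 5.4% | 2.7% | 5.0 |
| 0.10 | 18.1% | 10.5% | 5.2% | 10.0 |
| 0.20 | 33.0% | 19.7% | 10.1% | 20.0 |

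**3. Early events.** Let all risk R fall in the first 0.25 year, so h = −ln(1 − R)/0.25, with exposure uniform over 0-24 months. The percentage is the mean of 1 − exp(−h·min(t, 0.25)). A true 10% shows as 9.4% and a true 50% as 47.2%, a small loss. Here the pooled rate is the poor measure: the 50% case gives 85 per 100 subject-years, which read as constant over 2 years implies 1 − exp(−2 × 0.854) = 82%.

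**4. Interval denominator.** Take r = 0.20, exposure uniform over 0-24 months, and count any event starting in the interval. The share still exposed at interval start a (years) is 1 − a/2.

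| Months | whole Safety Set | share exposed at start | exposed at start | rate per 100 subject-years |
|---|---|---|---|---|
| 0-3 | 4.6% | 1 | 4.6% | 20 |
| >9-12 | 2.7% | 0.625 | 4.4% | 20 |
| >21-24 | 0.3% | 0.125 | 2.5% | 20 |

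On the whole Safety Set, a constant risk looks as though it vanishes. Using subjects still exposed removes most of that but not all, because many leave within the last interval. The rate is the figure to read.

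**5. One time base.** Counting events to 30 days after last dose over person-time to last dose inflates a true 20 per 100 to 21.5 (exposure uniform 0-24 months) or 23.1 (6 months each).

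**6. Precision.** With 200 subjects, uniform 0-24 months and r = 0.20, months 0-3 hold 45.7 event-free subject-years and 45.7 × 0.20 = 9.1 expected first events. Months >21-24 hold 2.2 and 0.4.

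**The case against.** This is a single-arm, descriptive study with no test, and the protocol never asked for person-time rates. SAP 1 follows the protocol unless otherwise specified, and SAP 3.2.3 and 9.2 assign TEAEs to periods, so the missing tables may still be intended. SAP 9.1 summarises exposure, including by region. SAP 9.2 lists AEs, SAEs, discontinuation AEs and deaths by subject, SAP 10.2.2.11 gives Kaplan-Meier estimates of discontinuation, and a DMC reviews safety. Protocol 2.5 describes mainly CNS events that ease over the first days of dosing, the pattern that loses least (step 3). Separate intervals also show time course more directly than cumulative ones.

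Much of this stands. Rates are an improvement, not a missed requirement, and separate intervals are defensible. Leaving out exposure categories can also be defended, because they condition on dropout. If TEAE withdrawal and other withdrawal each run at 0.20 per subject-year, every category under 24 months shows 0.20/0.40 = 50% TEAE withdrawal and completers show 0%, against a 24-month cumulative incidence of 0.5 × (1 − exp(−0.8)) = 27.5%.

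What does not stand is that the gap is filled. A general fallback clause beside an explicit table list leaves it unclear which tables to produce for a primary variable. The exposure summary is not linked to AEs, listings are not estimates, and the Kaplan-Meier analysis counts every discontinuation from the study. Early CNS events do not settle the pattern for withdrawal, serious or fatal ones.

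**Conclusion.** The point holds for TEAEs leading to discontinuation, serious TEAEs and fatal TEAEs: SAP 9.2 gives counts and percentages only, omits splits that protocol 12.3 planned, and SAP 3.9 is silent. It should be fixed, but it does not invalidate the analysis. The size cannot be known from the documents. Under the assumed sustained hazards of step 2, the same rate gives percentages that differ by a factor of two to three or more; for early events the effect is slight.

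Four stronger readings are tempting and not supported:
- That both primary safety variables are given only as crude percentages. All TEAEs keep an interval table and a dose-at-onset table.
- That leaving out the tables makes the percentages depend on exposure. They depend on it anyway.
- That study-period tables would have separated on-drug from post-dose events. The Taper Period includes a drug-free week (Protocol Table 5-1, footnote c), and SAP Table 3–3.21 merges Taper with Safety Follow-Up.
- That the SAP presents these percentages as 24-month risks. It does not.

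**What to change.** Keep the percentages. In SAP 9.2:
- For the any-event row of TEAEs, TEAEs leading to discontinuation, serious TEAEs and fatal TEAEs, overall and by region, add first-event rates per 100 subject-years with exact Poisson 95% intervals. Time at risk runs from first dose to the earlier of first event or last dose. Show the 3-month-interval rates beside the pooled rate.
- Add 3-month-interval tables for TEAEs leading to discontinuation and for serious TEAEs.
- For interval percentages, state that the denominator is subjects still exposed at interval start, and count any event starting in the interval. Restricting it to event-free subjects would hide later events in anyone with an early one.
- Report events after last dose separately, splitting at last dose and not by study period.

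In SAP 3.9, either restore the study-period and exposure-category tables of protocol 12.3, or declare and justify their replacement and the use of separate intervals.

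The cost is a few lines of text and modest programming for four event families, repeated by region and for Japan/non-Japan; dose dates and AE start dates are already collected. The drawbacks are sparse late intervals with wide confidence intervals, and a pooled rate that misleads for early events if shown alone.

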12.6 Handling of dropouts or missing data

The methods for handling dropouts will be described in the SAP. Safety and efficacy variables will be analyzed as they are available. Days with missing information will be ignored in the calculation of the seizure frequency. Since subjects will drop out at different times from the study, results will be presented by categories of duration of exposure.

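### SAP 9.2 leaves out the AE tables by study period and exposure duration that protocol 12.3 plans, offers only a partial 3-month table, and SAP 3.9 does not declare the change

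*SAP*

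**What the plan says.** Protocol 12.3 says that TEAEs will be "summarized by study period (Evaluation, Taper, and SFU) and reported for cumulative 3-month time intervals and categories of total duration of exposure". It then extends those splits: "Separate tables will be provided for AEs leading to withdrawal from the study and SAEs overall and by the subcategories listed above". Protocol 12.6 repeats the exposure split and gives the reason: "Since subjects will drop out at different times from the study, results will be presented by categories of duration of exposure".

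SAP 9.2 gives its own list of 14 AE tables. The one that is split by time is "Incidence of TEAEs by 3-month time interval during the Exposure Period". SAP 3.2.5 sets the windows for it: "For the analysis of AEs and safety variables, 3-month intervals will be derived for the Exposure Period". The windows are consecutive blocks, for example "Months >3-6 Days 91-180". The Exposure Period "Extends from the date of first dose until the last dose of PSL in EP0093" (SAP 3.2.3, table of analysis periods).

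The same table has a single row for "Taper Period/ Safety Follow-Up Period". It starts the day after Evaluation ends and runs to final contact, and no date separates its two parts. SAP 9.2 collects AEs until 30 days after the last intake.

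**The concern.** TEAE incidence and TEAEs leading to withdrawal are the two primary safety variables (protocol 4.1.1, SAP 2.2.1.1). If SAP 9.2 is followed as written, the tables that the protocol planned for them by period and by length of exposure are not produced.

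Two things would be lost from the tables. First, events during taper and after the last dose are pooled into whole-study counts, although protocol 9.3.8 asks for monitoring of withdrawal-related AEs during taper. Second, AEs cannot be read by how long subjects stayed on drug, which protocol 12.6 wanted because dropout times differ. A reader who has only the SAP would not know that anything had been removed, because SAP 3.9, the section for changes from the protocol, does not mention it.

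**Working it through.** **1. Planned against listed.** The inputs are protocol 12.3 for the plan and the 14 bullets of SAP 9.2 for what will be produced. Each cell counts the tables listed.

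| Split planned | All TEAEs | SAEs | AEs leading to withdrawal |
|---|---|---|---|
| Evaluation / Taper / SFU | 0 | 0 | 0 |
| Cumulative 3-month interval | 1, but disjoint and only to last dose | 0 | 0 |
| Category of total exposure | 0 | 0 | 0 |

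The plan has 3 event types × 3 splits = 9 combinations (the protocol states no number of tables). Eight have no table and one has a partial counterpart. Serious TEAEs and TEAEs leading to discontinuation each have a whole-study table without any of the three splits.

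**2. Events after the last dose.** Two of the 14 tables are limited to the Exposure Period: the 3-month table and the dose-at-onset table. The Exposure Period ends at the last dose and AE collection continues for 30 days, so events in those days are in neither table. Events on drug during taper are inside the Exposure Period but are not distinguished from Evaluation events.

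**3. Disjoint against cumulative.** A subject with the same preferred term starting on Day 30 and again on Day 120 is counted in Days 1-90 and again in Days 91-180, but only once cumulatively to Month 6. With subject counts n1 and n2 in the first two windows, the cumulative count lies between max(n1, n2) and n1 + n2. For assumed counts of 40 and 30, that is from max(40, 30) = 40 to 40 + 30 = 70. The disjoint table therefore does not fix the cumulative number of subjects. Event counts, where shown, do add across windows.

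**4. Exposure categories.** SAP 9.1 has six nested categories. With 30-day months (SAP 3.2.5) the thresholds are 90, 180, 270, 360, 540 and 720 days. They apply to the exposure summary and are not attached to any AE table.

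**5. Declared changes.** SAP 3.9 has six entries: Table 2-1, 3.10, 4.4, 10.2.1.8, 11 and 15. None concerns SAP 9.2 or AE tables. SAP 14.1, Change #28, logs how SAP 9.2 differs from its own previous text, which is not a declaration of departure from the protocol.

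**The case against.** The best defence is SAP 1, which keeps the protocol's analysis unless the SAP specifies otherwise. SAP 9.2 also assigns TEAEs to an analysis period by start date, and its list is not said to be exhaustive. This leaves some ambiguity but does not close the gap: SAP 9.2 sets out its own list of tables, and the merged Taper/SFU row does not define the three periods that the protocol names.

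It can also be said that cumulative in the protocol might mean successive. Even so, the period split, the exposure split and every split for SAEs and withdrawals would still be missing.

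Early termination of an open-label, descriptive study may well justify fewer tables. That is a reason to record in SAP 3.9, where it does not appear for these tables.

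Several stronger readings are tempting, and the documents do not support them:

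- *The three-way split cannot be programmed.* The end of Evaluation and the last dose are both defined and End of Taper is a scheduled visit. What is missing is a stated boundary.
- *Post-dose events cannot be identified.* SAP 3.2.2.2 already marks them with a + relative day in the listings. Where event counts are shown, the whole-study TEAE total minus the sum over the 3-month windows also gives their number. What is missing is a table.
- *Nested exposure categories hide early leavers.* Each subject has one total duration, so subtraction separates the groups: the Safety Set total minus the count at 3 months or more gives those under 3 months, and so on upward. The protocol does not ask for mutually exclusive categories.
- *Protocol 9.3.8 requires a taper table.* It concerns clinical monitoring, and for CIWA-B protocol 12.3 itself plans only a listing. The table commitment comes from the AE text of protocol 12.3.
- *Dropout is ignored.* Completer cohorts (SAP 3.2.6) address it for efficacy and Kaplan-Meier estimates (SAP 10.2.2.11) for retention. The gap is limited to the AE tables.

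**Conclusion.** The point stands as a mismatch between protocol and SAP in the AE tables, and it should be corrected. Of the 14 listed tables, 0 are by study period, 0 by exposure category and 1 by 3-month interval, the last being partial. SAP 3.9 declares none of this.

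Its weight is moderate. A reader might infer that the safety results would be biased or that the primary safety variables go unreported. Neither follows: the whole-study TEAE, serious TEAE and discontinuation tables and the AE listings remain, and no estimate changes. What is lost is tabulated information on when events occur relative to taper, last dose and length of exposure.

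The conclusion rests on reading the SAP 9.2 list as the tables to be produced. The 40-to-70 range rests on assumed counts, applies to subjects only, and shows just that the disjoint table does not determine the cumulative one.

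**What to change.** **SAP 3.2.3.** Define Taper and SFU as separate periods. Taper runs from the day after the end of Evaluation to the actual End of Taper Visit. If that visit is missing, end Taper at last dose + 7 days (SAP 2.3 places the visit 1 week after the last intake), but only when that date falls after the end of Evaluation. Otherwise, and for subjects who skip taper, there is no Taper period. The condition is needed: if, say, the last dose is on Day 100 and the EDV on Day 110, Taper would start on Day 111 and end on Day 107. Use the existing last-dose date to show on-drug and post-last-dose events separately. This also covers subjects without an EOS or EDV visit, whose Evaluation Period runs to last contact.

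**SAP 9.2.** Add tables for TEAEs, serious TEAEs and TEAEs leading to discontinuation:

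- by Evaluation, Taper and SFU, with subjects entering each period as denominator;
- by cumulative 3-month interval, each subject counted once from first dose;
- by total-exposure category; the SAP 9.1 thresholds plus a group under 3 months are sufficient.

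**SAP 3.9 and 15.** List any of these tables that will not be produced, with the reason (for example early termination), and exempt sparse ones from the Japan and non-Japan repeat.

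**Cost.** SAP wording and up to 3 × 3 = 9 tables from dates already collected. With SAP 15 that becomes up to 9 × 3 = 27 outputs (overall, Japan, non-Japan) unless some are exempted. Some will be sparse, such as AEs leading to withdrawal in Taper or SFU, because Evaluation normally ends at the EDV.

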resistant to current available drug therapies. The efficacy of PSL has been demonstrated in 10 nonclinical models of epilepsy and a more recently completed Phase 2 study in patients with highly drug resistant epilepsy revealed clinically meaningful reductions in seizure frequency. Study participants in the PSL/PSL treatment group were 4.14 times more likely to achieve a $\geq 75\%$ reduction from the Baseline Period in focal seizure frequency during the 2-week Inpatient Period compared with study participants in the Placebo/PSL treatment group ($p=0.0679$). The 75% responder rate (RR) approached statistical significance and was clinically meaningful. The median percentage of seizure-free days during the 2-week Inpatient Period in the PSL/PSL treatment group (57.14%) was greater than in the Placebo/PSL treatment group (21.43%). Therefore, based on the evidence demonstrating superior seizure control compared with other marketed AEDs across several preclinical models of epilepsy (Leclercq et al, 2017), and the results of the proof of concept study, EP0069 (Muglia et al, 2017), treatment with PSL has the potential to benefit an underserved epilepsy population with high unmet medical need.

Overall, the clinical pharmacology and clinical studies in drug-resistant epilepsy demonstrated the AE profile of PSL is generally consistent with the pharmacological activity of the product, and in the context of early dose-escalation studies in healthy study participants and patients with epilepsy. The safety findings to date suggest that the AEs experienced by study participants receiving single and repeated doses of PSL are limited principally to CNS effects. The AEs tend to be dose-related in frequency and intensity, self-limiting, and tend to decrease in intensity over the first few days of dosing.

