### Evaluation Period

The Entry Visit (EV, Visit 1) will be done the same day as the last visit of the parent study. After the Entry Visit (EV, Visit 1), subjects will return to the clinic for visits as follows:

- Every 2 weeks during Month 1
- Every month during Month 2 and Month 3
- Every 3 months after Month 3 to the end of Year 2

Dose adjustment of PSL and/or concomitant AEDs and/or settings to neurostimulation devices is allowed at any time during the study, if seizure control is insufficient, or in case of safety or tolerability issue. Subjects who are not able to tolerate or who do not benefit from the PSL treatment may be tapered off PSL and withdrawn from the study.

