## 3.6 Treatment assignment and treatment groups

The individual starting dose of each subject will be the one recommended at the end of the parent study. Further individual dose adjustments are allowed between 100mg/day up to a maximum of 800mg/day to the extent possible with combination of tablet strengths available (ie, 25mg, 100mg, and 200mg).

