### 9.1 Extent of exposure

The overall duration of exposure of the study will be calculated as the date of last dose of PSL minus the date of first dose of PSL (Section 3.2.2.1) in EP0093 plus 1 day.

Modal daily dose of a subject will be calculated as the daily dose the subject received for the longest duration during EP0093. In the event of a tie, the modal dose will be set to the lower of the tied doses. Modal daily dose will be categorized as  $\leq 200$ mg/day,  $> 200$ mg/day to  $\leq 400$ mg/day,  $> 400$ mg/day to  $\leq 600$ mg/day, and  $> 600$ mg/day.

The duration of exposure will be summarized overall and by modal dose for the SS and by region:

- Cumulative months of exposure: duration of exposure in days will be summarized. Duration of exposure will also be categorized into the following cumulative months categories of exposure:  $\geq 3$  months,  $\geq 6$  months,  $\geq 9$  months,  $\geq 12$  months,  $\geq 18$  months, and  $\geq 24$  months.

Listings will include the study medication exposure per subject and the administration of study medication per dispense interval. Data collected on the Prescribed Padsevonil Dose CRF will be listed.

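### The TEAE table by dose at onset has no time-at-dose denominator, so its band percentages are confounded by how long subjects spend in each dose band

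*SAP*

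**What the plan says.** SAP 9.2 introduces its list of adverse event tables with "The following tabular summaries will be presented for the SS". One entry is "Incidence of TEAEs by Dose at Onset", in four bands during the Exposure Period. For content, the section says: "Summary tables will contain counts of subjects, percentages of subjects in parentheses and the number of events where applicable". It does not say whether a band percentage is taken over the whole Safety Set or over subjects who were ever in that band, and it plans no rate per unit of exposure.

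Dose is not fixed. Under the Evaluation Period text of SAP 2.3, a change of dose "is allowed at any time during the study, if seizure control is insufficient, or in case of safety or tolerability issue". SAP 3.6 gives the range: "Further individual dose adjustments are allowed between 100mg/day up to a maximum of 800mg/day". That range covers all four bands, so one subject can contribute time to several.

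SAP 9.1 summarises duration of exposure overall, by modal dose and by region. It defines the modal dose as follows: "Modal daily dose of a subject will be calculated as the daily dose the subject received for the longest duration during EP0093". This puts each subject in one band for the whole study. Time accrued in each band is not summarised.

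**The concern.** The chance that a subject has at least one TEAE starting in a band grows with the time spent there, even when the risk per unit time is the same at every dose. A table of subject percentages by band then mixes the risk at that dose with the length of stay. If the Safety Set is the denominator, it also mixes in the share of subjects who ever reach the band. Such a table can show a dose pattern that does not exist or flatten one that does.

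Time at dose is likely to be uneven here. Protocol 5.3 describes a transition dose of 400 mg/day for subjects coming from 800 mg/day, which falls in the second band. The Exposure Period may include the taper (SAP 3.2.3), which has three weeks on drug (SAP Table 2-1, footnote c), so tapering subjects can add short stays in lower bands. SAP 3.9 also records early termination of the study.

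Readers will want to use this table. Protocol 2.5 says of PSL: "The AEs tend to be dose-related in frequency and intensity". The primary objective concerns safety at individualised doses from 100 to 800 mg/day, and no other table in the SAP 9.2 list splits TEAEs by dose level.

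**Working it through.** The documents give no TEAE rate by dose and no time at dose, so there is no plan figure to reproduce. The check is an illustration over a range of assumptions.

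**Inputs from the documents:** four dose bands; subject percentages as the measure; dose changes allowed across all bands; a taper with three weeks on drug.

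**Assumed inputs:** a constant hazard h of first onset in a band, from 0.1 to 1.0 per year; a time t in the band that is the same for everyone who enters it; and the share of subjects ever in the band.

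**Formulas**
- Percentage of subjects ever in the band with a TEAE starting there: 100 × (1 − exp(−h × t)).
- Percentage of the Safety Set: the same figure multiplied by the share ever in the band.
- First events per subject-year: (1 − exp(−h × t)) divided by the mean time at risk, (1 − exp(−h × t)) / h. This equals h, whatever t is.

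**Step 1: equal hazard, unequal time.** The reference band has t = 1 year. The other has 1/2, 1/5 or 1/10 of that. For h = 0.2 the figures are 1 − exp(−0.2) = 18.1%, 1 − exp(−0.1) = 9.5%, 1 − exp(−0.04) = 3.9% and 1 − exp(−0.02) = 2.0%.

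| Hazard per year, both bands | 1 year | 1/2 year | 1/5 year | 1/10 year |
|---|---|---|---|---|
| 0.1 | 9.5% | 4.9% | 2.0% | 1.0% |
| 0.2 | 18.1% | 9.5% | 3.9% | 2.0% |
| 0.5 | 39.3% | 22.1% | 9.5% | 4.9% |
| 1.0 | 63.2% | 39.3% | 18.1% | 9.5% |

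Within each row the risk per unit time is identical. The size depends on the assumptions; the direction does not.

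**Step 2: a true doubling of hazard.** Band >200–400: h = 0.2, t = 1. Band >600: h = 0.4, t = 0.5. Both give 1 − exp(−0.2) = 18.1%, so the doubling disappears among subjects ever in the band. With assumed shares of 90% and 20% ever in the band, the Safety Set percentages are 0.90 × 18.1 = 16.3% and 0.20 × 18.1 = 3.6%, so the order reverses.

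**Step 3: all four bands at an equal hazard of 0.2.** Assumed times are 3 weeks (21/365.25 = 0.057 year), 1, 0.75 and 0.5 years; assumed shares are 60, 90, 40 and 20%.

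| Band (mg/day) | % of ever in band | % of Safety Set | First events per 100 subject-years |
|---|---|---|---|
| ≤200 | 1.1 | 0.7 | 20 |
| >200–400 | 18.1 | 16.3 | 20 |
| >400–600 | 13.9 | 5.6 | 20 |
| >600 | 9.5 | 1.9 | 20 |

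Neither denominator removes the distortion. If the hazards are instead 0.2, 0.2, 0.3 and 0.4, the rates are 20, 20, 30 and 40 per 100 subject-years, which recovers the true pattern under the constant-hazard assumption. Event counts do not help on their own, because without subject-years they also grow with time in the band.

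**The case against.** The table is descriptive. The primary safety variables are overall incidence of TEAEs and of TEAEs leading to withdrawal, neither split by dose, and no test or decision rule in these documents uses the by-dose table. That stands, and it limits the point to how one table is read. A reader might infer that the primary safety result is compromised; the documents do not support this.

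A reader might also infer that the percentages measure time instead of risk. That goes too far, because they mix the two. Nor is this the only output that bears on dose: SAP 9.2 also tabulates TEAEs leading to dose reduction, and SAP 9.1 gives duration by modal dose in the same four bands. Neither, however, splits TEAEs by dose level or gives time in each band.

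Dose movement has limits. Protocol 7.2 allows adjustment after 1 week and normally by no more than 200 mg/day per week, except in an emergency. Subjects can still cross bands within those limits.

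The strongest objection is that rates per subject-year do not make the bands comparable. Dose is changed because of tolerability or poor seizure control, so time in a band depends on outcome. The sentence in Protocol 2.5 on dose-related AEs adds that they are self-limiting and ease over the first days of dosing. That concerns intensity, not onset, but it gives reason to doubt a constant hazard. If onsets cluster after entry or a dose change, rates could be inflated in briefly held bands and diluted in long-held ones. This stands, and it is why the rates need a caution beside them.

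The planned listings of doses and AEs, the event counts and the table by 3-month interval soften the problem, since rates could be derived from data already held. They do not supply the missing denominator.

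**Conclusion.** The point holds as one of interpretation. The by-dose percentages have no stated band denominator and no time at dose, so they are confounded by time in the band and, over the Safety Set, by the share of subjects reaching it. With equal hazards between 0.1 and 1.0 per year, a twofold difference in time alone gives anything from 9.5% against 4.9% to 63.2% against 39.3%. Hazards, times and shares are all assumed; the actual distortion depends on dose histories that the documents do not report. The correction is worth making because this is the one planned table that splits TEAEs by dose level and the change is cheap. It should not be read as making a dose-response comparison possible, since band membership would still depend on outcome.

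**What to change.** - **SAP 9.1:** tabulate, for each of the four dose bands, the number of subjects ever in the band and the subject-years accrued in it, alongside the modal-dose summary.
- **SAP 9.2:** keep the crude counts, state the denominator of the band percentages, and add events and first events per 100 subject-years at dose.
- **Footnote to the table:** say that dose was changed in response to tolerability and seizure control, and that onset may cluster early after entry or a dose change, so the rates are not a dose-response comparison.

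The cost is SAP wording and one derivation. Assigning a dose at onset already needs dated dose histories, and SAP 9.1 lists prescribed-dose and administration data, so no new collection is needed. The downside is that the rates assume a roughly constant hazard and can be unstable or inflated in briefly held bands. Showing the subject-years beside each rate lets the reader see where that applies.
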